Appendix A. Conventions for Clinical Data That Require Imputation for Partial or Missing Date.....	23
Appendix B. Wilson's Score Method with Continuity Correction in Calculating the 95% Confidence Intervals for Difference in 2 Independent Proportions	25

Table of Abbreviations

Abbreviation/Acronym	Definition
AE	Adverse event
CI	Confidence interval
CR	Complete response
CRF	Case report form
CT	Computerized Tomography
CTC	Common Toxicity Criteria
CTCAE	Common Toxicity Criteria for Adverse Events
DMP	Data management plan
DOR	Duration of Response
DRR	Durable Response Rate
DTP	Data transfer plan
ECOG	Eastern Cooperative Oncology Group
eCRF	Electronic Case Report Form
EOI	Event of Interest
HR	Hazard ratio
HSV	Herpes simplex virus
HSV-1	Herpes simplex virus type 1
IP	Investigational product
IPD	Important protocol deviation
IVRS	Interactive Voice Response System
KM	Kaplan-Meier
MedDRA	Medical Dictionary for Regulatory Activities
ND	Not done
NPV	negative predictive value
OR	Objective response (CR or PR)
ORR	Objective response rate
PD	Progressive disease
PFU	Plaque-forming unit
PPV	positive predictive value
PR	Partial response
PT	Preferred term
qPCR	Real-time polymerase chain reaction
SAE	Serious adverse event
SAP	Statistical analysis plan

Abbreviation/Acronym	Definition
SD	Stable disease
SMQ	Standardized MedDRA Queries
SOC	System organ class
SOP	Standard Operating Procedure
TTF	time to treatment failure
UE	Unevaluable for tumor response
ULN	Upper limit of normal
WHO	World Health Organization
WHODRUG	World Health Organization Drug Dictionary

1. Introduction

The purpose of this statistical analysis plan (SAP) is to provide details of the statistical analyses that have been outlined within the protocol 20120325 entitled “A Phase 2, Multicenter, Open-label, Single-arm Trial to Evaluate the Correlation Between Objective Response Rate and Baseline Intratumoral CD8+ Cell Density in Subjects With Unresected Stage IIIB to IVM1c Melanoma Treated with Talimogene Laherparepvec”.

The scope of this plan includes the primary analysis that is planned and will be executed by the Biostatistics department at Amgen unless otherwise specified. A separate SSAP will be prepared for the exploratory objectives and these analysis may be reported separately.

2. Objectives

Primary Objective:

The primary objective of the statistical analysis is to explore the correlation between a baseline immunoprofile (ie, intratumoral CD8+ cell density) and objective response rate (ORR) in subjects with unresected stage IIIB to IVM1c melanoma treated with talimogene laherparepvec.

Secondary Objective(s):

The secondary objectives are as follows:

- to explore the correlation between baseline intratumoral CD8+ cell density and durable response rate (DRR), duration of response (DOR), and changes in tumor burden
- to explore the correlation between changes in intratumoral CD8+ cell density during treatment and ORR, DRR, DOR, and changes in tumor burden
- to evaluate ORR, DOR, time to treatment failure (TTF), DRR, OS, and change in tumor burden during treatment
- to evaluate the safety and tolerability of talimogene laherparepvec

Exploratory Objective(s):

The exploratory objectives are as follows:

- to investigate the correlation between the changes in the population of tumor specific cytotoxic T cells and immunoscore during treatment and clinical response

C
C
I

3. Protocol Overview

3.1 Protocol Design

This is a phase 2, multicenter, open-label, single-arm study [REDACTED]

Subjects will be treated with talimogene laherparepvec until the subject has achieved a complete response, all injectable tumors have disappeared, clinically significant (resulting in clinical deterioration or requiring change of therapy) disease progression beyond 6 months of treatment, per modified World Health Organization (WHO) response criteria (WHO handbook for reporting results of cancer treatment, 1979; refer to Appendix D of the protocol), or intolerance of study treatment, whichever occurs first.

Subjects will be followed for safety 30 (+ 7) days after the last dose of talimogene laherparepvec and for survival every 12 weeks (\pm 28 days) for up to approximately 24 months after the last subject is enrolled. Thereafter, subjects will be followed under an ongoing separate registry protocol (Study 20120139) for the long-term survival follow-up of subjects treated with talimogene laherparepvec. The registry protocol will also monitor for late and long-term adverse events thought to be potentially related to talimogene laherparepvec.

Blood and tumor tissue samples will be collected at timepoints outlined in the Schedule of Assessments (Table 2 of the protocol). Tumor biopsies will be performed on an uninjected lesion on day 1 of week 1, on a different uninjected lesion at week 6 (if available), and at disease progression (PDn or PDr beyond 6 months of treatment) on the lesion responsible for PD as outlined in Section 7.2.2 of the protocol. Blood and tumor tissue samples will be analyzed to explore if an immunoprofile at baseline and its change during treatment is correlated with the objective response rate in subjects with unresected stage IIIB-IVM1c melanoma treated with talimogene laherparepvec. The primary immunoprofile will be tumor cell CD8+ density.

For a full description of the protocol design, please refer to Section 3.1 of the protocol.

3.2 Sample Size

Participants in this clinical investigation shall be referred to as "subjects". Approximately 110 subjects will be enrolled in the study. Refer to Section 10.2 of the protocol for sample size considerations.

4. Protocol Endpoints and Covariates

4.1 Protocol Endpoints

4.1.1 Primary Endpoint

- Correlation between a baseline immunoprofile (ie, intratumoral CD8+ cell density) and objective response rate (ORR)

4.1.2 Secondary Endpoints

- Correlation between a baseline immunoprofile (ie, intratumoral CD8+ cell density) and durable response rate (DRR), and duration of response (DOR), and changes in tumor burden
- Correlation between changes in an immunoprofile during treatment (in injected and uninjected lesions) and ORR, DRR, DOR, and changes in tumor burden
- Efficacy Endpoints: ORR, DOR, time to treatment failure (TTF), DRR, OS, and change in tumor burden during treatment
- Safety Endpoints: subject incidence of treatment-emergent and treatment-related adverse events (including all adverse events, grade ≥ 3 adverse events, serious adverse events, fatal adverse events, events of interest, adverse events requiring the discontinuation of study drug), clinically significant laboratory changes, and incidence of symptomatic herpetic lesions that are positive for talimogene laherparepvec

4.1.3 Exploratory Endpoints

- Correlation between the changes in the population of tumor specific cytotoxic T cells during treatment and clinical response

C
C
I

5. Hypotheses

No formal statistical hypothesis will be tested.

6. Definitions

The definitions of primary endpoints are provided in [Section 4](#).

Additional definitions are as follows:

Enrollment date

The date subject is enrolled to the study. A subject will be considered enrolled when the investigator confirms that the subject has met all eligibility criteria and the subject is registered as enrolled in the ETO system.

Investigational Product

Investigational product (IP) refers to talimogene laherparepvec in this study.

Study Drug

Study drug refers to talimogene laherparepvec in this study.

Last IP Dose Date

Last IP Dose Date for each subject is defined as the latest date IP is administered in this study.

End of IP Admin Date

End of IP Admin Date for each subject is defined as the date the decision was made to end IP as recorded on the End of IP CRF page in this study.

Screening Phase

The screening phase is the time period after subject signing off the informed consent form and before enrollment when study-specific laboratory tests and procedures are performed, and medical history is reviewed to confirm subject eligibility for the study.

Study Day

Study day is calculated from the first day the study drug is administered to the subject.

Study day = visit date – first dose date +1 if visit date is on or after the first dose date.

Study day = visit date – first dose date, if visit date is before the first dose date.

Study Day 1

Study day 1 is the first day the study drug is administered to the subject. The day before study day 1 is study day '-1'.

Baseline

Baseline in general refers to study day 1. The baseline value of a parameter (e.g., vital signs, laboratory tests, and tumor measurement) is considered to be the latest value prior to receiving the study drug (i.e., on or prior to the first date of dosing).

Disease Control Rate(also called the Clinical Benefit Response Rate)

[figure not shown]
Disease control rate is the proportion of subjects that have a best overall response in one of the following: CR/ PR/SD.

Time to Treatment Failure (TTF)

Time to treatment failure is calculated from first dosing until one or more of the following: (1) clinically relevant disease progression(PDr); (2) death from any cause; (3) non-clinically relevant disease progression (PDn) associated with a requirement for

alternative therapy as the reason for ending treatment or start of new anti-cancer therapy. Subjects without an event will be censored at their last evaluable tumor assessment.

This TTF definition is a modified definition of progression free survival (PFS). We do not penalize stopping treatment for CR or lack of injectable disease. In addition, the confirmation of PD is not required.

CCI

Treatment Period

Treatment period is defined as the period between the first date of IP administration in the study and 30 days after the last IP administration in the study.

Treatment-emergent Adverse Events

Treatment-emergent adverse events are defined as any adverse event occurring after initiation of the first dose of IP through 30 days after the last administration of IP in the study. Adverse events that occur on the same day as the first dose date of IP will be treated as treatment-emergent events unless indicated otherwise. (For example, if an event occurs on the same date as the first administration of talimogene laherparepvec and the check box indicating prior to the first dose of IP is checked, then the event will not be counted as a treatment-emergent AE).

Exposure-adjusted Subject Incidence

Exposure-adjusted subject incidence is defined as the number of subjects experiencing a specific event divided by their total subject-time at risk (summation of the time from first drug exposure to first event for subjects with at least one event or to death/end of study/30 days after last IP dose, whichever occurs first for subjects without the event).

Exposure-adjusted Event Rate

Exposure-adjusted event rates is defined as the number of occurrences that subjects experience of a specific event divided by their total subject-time at risk (summation over all subjects). Multiple occurrences of the same event for a subject are counted as events. For each subject, the time at risk will be defined as the start date of IP to death/end of study/30 days after last IP dose, whichever occurs first.

On-study Surgery/procedure

On study surgeries or procedures are defined as surgeries or procedures performed during the treatment period.

[figure not shown]
On-study Death

Deaths of all causes that occur any time during the study are defined as on-study deaths. This may include deaths that occur beyond the end of the treatment period. Note that this study has a long-term survival follow-up after the safety follow-up, deaths that occur after the study long-term survival follow-up will be reported in study, 20120139, which is the registry study for long-term follow up of clinical trial subjects who have completed talimogene laherparepvec treatment.

7. Analysis Subsets

Safety Analysis Set: The safety analysis set will include all subjects who have received at least 1 dose of talimogene laherparepvec. The efficacy analysis and safety analysis will be performed on the safety analysis set.

CCI

Reactive Swab Analysis Set

Subjects who are enrolled, receive at least one dose of talimogene laherparepvec, and have at least one swab sample collected from lesions that are suspected to be herpetic

in origin. This analysis set is used to examine the number of subjects with a lesion suspected to be herpetic, and detection of talimogene laherparepvec DNA by qPCR in lesions suspected to be herpetic in origin.

8. Covariates and Subgroups

The following covariates may be used to examine efficacy and safety in subgroups or in multivariate analyses:

- Region, if applicable (by countries)
- Age at baseline: < 50, ≥ 50; < 65, ≥ 65; < 75, ≥ 75 years
- Disease stage at baseline: IIIB and IIIC vs IVM1a vs IVM1b vs IVM1c
- Baseline LDH ≤ ULN vs > ULN
- Sex (Female vs Male)
- ECOG (0 vs 1)

9. Interim Analysis

No interim analysis is planned.

10. Data Screening and Acceptance

10.1 General Principles

The objective of the data screening is to assess the quantity, quality and statistical characteristics of the data relative to the requirements of the planned analyses. The database will be subject to edit checks outlined in the protocol-specific Data Management Plan (DMP). Data with inconsistencies and suspicious values will be queried and resolved before the database lock.

10.2 Data Handling and Electronic Transfer of Data

Amgen's Clinical Data Management (CDM) department will provide all data to be used in the planned analyses. This protocol will use the RAVE database. In addition, blood and/or tumor tissue samples for **CCI** [REDACTED], HSV antibody serostatus samples, and swab samples collected from lesions suspected to be herpetic in origin, will be processed and analyzed by a vendor of Amgen. Analysis results of these samples will be transferred to Amgen CDM on a regular basis as per a Data Transfer Plan (DTP) and will be stored on the CDM server.

10.3 Handling of Missing and Incomplete Data

Adverse events with missing severity, seriousness, and/or possible relationship to talimogene laherparepvec should not be imputed for study analyses. Missing data should be queried and resolved. **CCI** [REDACTED]

CCI

Partial or missing dates of adverse events and concomitant medications will be imputed.

CCI

10.4 Validation of Statistical Analyses

Programs will be developed and maintained, and output will be verified in accordance with current risk-based quality control procedures.

Tables, figures and listings will be produced with validated standard macro programs where standard macros can produce the specified outputs.

The production environment for statistical analyses consists of Amgen-supported versions of statistical analysis software, for example the SAS System version 9.3 or later.

11. Statistical Methods of Analysis

11.1 General Principles

The main goals of this analysis are: (1) to better understand the distribution of intratumoral CD8+ cell density in the overall population and in subgroups; (2) to explore associations among baseline/change in intratumoral CD8+ cell density and efficacy endpoints; and (3) to explore the clinical potential utility of intratumoral CD8+ cell density cut-off values for patient selection.

Changes in intratumoral CD8+ cell density will be analyzed overall and separately for injected and uninjected lesions.

In principle, mean, standard deviation, median, first and third quartiles, minimum and maximum will be calculated for continuous variables; frequency count and percent will be calculated for binary and categorical variables. P-values will be used mainly as a descriptive measure suggesting comparative strength of association rather than to test hypotheses. Accordingly, nominal p-values will be generated with no adjustment for multiplicity. Analyses will be based on the Safety Analysis Set unless otherwise specified.

CCI

. The

following are some general principles which will be followed to handle such issues for efficacy analyses.

- It is desirable for subgroups to have 10 or more subjects for each dichotomization or categorization scheme, though judgment maybe applied.
- Analyses will be more carefully considered for robustness of results (e.g., K-M curves, model building, comparison between subgroups) when some subgroups have a small number of subjects and/or when there are few events for time-to-event endpoints..

CCI [REDACTED]
[REDACTED]
[REDACTED]
[REDACTED]
[REDACTED].

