10.2 Sample Size Considerations

All analyses will be descriptive with no formal hypothesis testing. The sample size was selected based on practical considerations. The primary objective of the study is to assess whether baseline intratumoral CD8+ cell density is correlated with the likelihood of response to talimogene laherparepvec. Analyses for the objective will focus on whether the response rate varies with baseline intratumoral CD8+ cell density. The functional manner in which the response rate may vary with the biomarker is unknown, therefore multiple functional relationships may be examined. It is assumed that 100 subjects (approximately 91% of the enrolled) will have an evaluable baseline intratumoral CD8+ cell density. The adequacy of the sample size was evaluated for one of several possible analyses that evaluates whether the response rate is positively correlated with a high baseline intratumoral CD8+ cell density where a low and high biomarker is defined as a value below versus at or above the sample median, respectively. A one-sided Fisher's Exact test will be performed at a 5% nominal level to explore the hypothesis that the response rate is equal regardless of baseline intratumoral CD8+ cell density. The overall ORR is assumed to be 26.4%. The power for the test will depend on the true response rates in the biomarker subgroups. Assuming the true response rate is 13.2% in the biomarker low subgroup, and 39.6% in the biomarker high subgroup, the power will be 88% to detect a positive association.

A secondary objective of this study is to estimate the objective response rate. Based on the analysis of the OPTiM study, the overall response rate for stage IIIB/C and IVM1c is assumed to be around 26.4% where, among responders, the probability of response onset after 12 months was < 5%. The expected exact 95% CIs for various true ORRs are listed in [Table 4](#). The expected width of the 95% CI is around 18% under these scenarios.

Table 4. Expected 95% Confidence Intervals by Various True ORRs

Subjects enrolled (N)	True	Expected 95% CI (width)
110	20%	13% - 29% (16%)
	30%	22% - 39% (18%)
	40%	31% - 50% (19%)
	50%	40% - 60% (19%)

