Another secondary objective is to explore the correlation between changes in intratumoral CD8+ cell density during treatment and objective response rate. The primary focus will be on changes in tumor cell CD8+ density. It is assumed that 55 subjects (approximately 50% of all enrolled) will be evaluable with a pre- and on-treatment lesion biopsy that is sufficient to evaluate biomarker changes in uninjected lesions. In addition to correlating biomarker changes with objective response, Pearson's correlation coefficient (r) will also be estimated between the biomarker change and the maximum decrease in index lesions. With 55 evaluable subjects, a value of $r \leq 0.30$ will be rejected at a nominal 1-sided 5% significance level with an observed $r > 0.49$ for which the power will be $> 80\%$ given a true value for $r \geq 0.60$.

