10.4.2 Secondary Endpoint (s)

Multiple biomarkers will be examined to assess the correlation between their baseline value and DRR, DOR, and changes in tumor burden as well as the changes in their value during treatment with ORR, DRR, DOR, and changes in tumor burden. The functional manner in which the ORR, DRR, DOR, and change in tumor burden may vary with each biomarker is unknown, therefore multiple functional relationships will be examined to assess overall evidence of an association. Combinations of biomarkers may be explored to assess their predictive value for patient selection. Example analyses include, but are not limited to: (a) the correlation of baseline value as a continuous variable with the odds of OR, DR or the hazard of ending response; (b) a trend test for an increasing ORR, DRR with pre-specified, ordered biomarker categories, (c) a test that the ORR, DRR or hazard of ending response is greater between subgroups of subjects with a high vs. low baseline biomarker value for all possible cut-points for a minimum high biomarker value, (d) a receiver operating characteristic (ROC) analysis (categorical and continuous biomarker values), and (e) calculation of negative predictive value (NPV) and positive predictive value (PPV) for each candidate cut-point for ORR and DRR.

In order to evaluate the correlation between changes in biomarkers during treatment and the effect of treatment on measurable lesions, Pearson's correlation coefficient (r) will be estimated between the biomarker change and the maximum decrease in index lesions, in addition to correlating biomarker changes with ORR/DRR using logistic regression, and duration of response using Cox model regression.

Overall survival (OS), duration of response and time to treatment failure will be summarized by K-M methods. Durable response rate and objective response rate will be presented with 95% CI.

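### SAP 11.1 reads relative strength of association from p-values, yet the planned analyses differ in size by design, so a comparison of p-values across them favours the larger sets

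*SAP*

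**What the plan says.** SAP 11.1 (General Principles) sets the role of p-values: "P-values will be used mainly as a descriptive measure suggesting comparative strength of association rather than to test hypotheses". It adds that "nominal p-values will be generated with no adjustment for multiplicity". The same section names as goals the association of baseline density and of its change with efficacy, and the possible use of cut-offs for selecting patients.

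Protocol 10.2 gives the expected sizes. For baseline: "It is assumed that 100 subjects (approximately 91% of the enrolled) will have an evaluable baseline intratumoral CD8+ cell density". For change: "It is assumed that 55 subjects (approximately 50% of all enrolled) will be evaluable with a pre- and on-treatment lesion biopsy". It also says that "The overall ORR is assumed to be 26.4" percent. Protocol 10.4.2 relates biomarker change to "duration of response using Cox model regression", an analysis that only responders can enter.

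Effect measures are planned too. Protocol 10.4.2 lists the odds of response against continuous baseline density, the hazard of ending response, ROC analysis, predictive values for each candidate cut-point and Pearson's r. SAP 11.3 plans exact CIs for rates and Wilson score CIs for differences between rates. Most of SAP 11.4, which covers the correlation of response with CD8+ density, is redacted.

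**The concern.** A p-value combines the size of an effect with the amount of information behind it. When two analyses have the same N and the same group split, the smaller p does go with the stronger association. When one analysis has nearly twice the subjects of another, it need not.

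The study tests no formal hypothesis (SAP section 5), so its product is a description of which associations look strongest. If a reader follows SAP 11.1 when setting baseline density beside change in density, or objective response beside duration of response, the larger set has an advantage unrelated to biology. The wrong time point or endpoint could be reported as the more informative one. Multiplicity adjustment would not cure this, because adjusted p-values depend on N in the same way.

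**Working it through.** **Inputs.** From protocol 10.2: 100 subjects for baseline and 55 for change; median split; one-sided Fisher's exact test at 5%; response rates 13.2% (low) and 39.6% (high); stated power 88%; for correlation, n=55, null r=0.30, critical r 0.49, power above 80% at r=0.60. Assumed here: a split of 28 and 27 for the 55; a stronger-change scenario of 8% vs 45% (mean 26.5%, close to the assumed overall 26.4%); independent draws for the two analyses.

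**The plan's own figures.**
- Summing over all outcomes of two binomials (50 and 50), the one-sided Fisher test has power 88.4%. The stated 88% is reproduced.
- Critical r = tanh(atanh 0.30 + 1.645/√52) = tanh(0.3095 + 0.2281) = 0.491. Power at r=0.60 is Φ((0.6931 − 0.5376)·√52) = Φ(1.12) = 86.9%. Both agree with the protocol.

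**Number of responders.** This is not printed. 0.264 × 100 = 26.4; 0.264 × 110 = 29.0; 0.264 × 55 = 14.5. Hence about 15 to 29.

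**Same correlation, different N.** With t = r·√((N−2)/(1−r²)) and a Fisher-z interval, r = 0.30 gives:

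| N | t | two-sided p | 95% CI for r |
|---|---|---|---|
| 100 | 3.11 | 0.0024 | 0.11 to 0.47 |
| 55 | 2.29 | 0.026 | 0.04 to 0.52 |
| 26 | 1.54 | 0.136 | −0.10 to 0.62 |

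The strength is identical in each row. To match the p-value in the first row, r must be 0.40 at N=55 and 0.57 at N=26.

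**Duration of response.** For a Cox comparison of two equal groups, z ≈ √(d/4)·|ln HR|, where d is the number of responses that have ended. With an assumed HR of 0.50, d=26 gives z=1.77 and p=0.077; d=13 gives z=1.25 and p=0.21. The hazard ratio is the same in both.

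**Same response rates, different N.** At 13.2% vs 39.6%:
- Median one-sided Fisher p is 0.0025 at N=100 and 0.023 at N=55, about ninefold apart. Power is 88% and 62%.
- The larger set has the smaller p in 74% of trials, but the larger observed rate difference in 50%, as it should when the effects are equal.

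**Change truly stronger.** Baseline 13.2% vs 39.6% (26.4 points) at N=100; change 8% vs 45% (37 points) at N=55:
- p places baseline first in about 48% of trials.
- The observed difference places baseline first in about 22%.

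In the trial, subjects with both biopsies would be contained in the baseline set, so the two analyses would be correlated. The percentages are therefore indicative. The dependence of p on N does not rest on the independence assumption.

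**The case against.** **The sentence mainly disclaims testing.** It is hedged, its contrast is with hypothesis tests, and no readable text orders the baseline, change and responder-only analyses by p. This stands, so a reader should not infer that the SAP lays down an explicit ranking rule. But the sentence does give p-values the task of suggesting relative strength, under principles that govern all these analyses.

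**Effect measures are planned, and SAP 11.4 cannot be read.** This also stands. One might infer that strength will be reported by p-values alone; the documents do not support that. What the readable text lacks is a statement that estimates are the basis for comparison. SAP 11.1 gives that role to p-values.

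**One might infer that the order of p-values follows sample size instead of strength.** That goes too far. An r of 0.60 at N=26 (p=0.0012) ranks ahead of r=0.30 at N=100 (p=0.0024). In the scenario above, p still favours the stronger marker in slightly more than half of trials. N and split matter as well as strength; they do not replace it.

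**One might infer that p-values should also be barred from comparing cut-points**, since protocol 10.4.2 scans "for all possible cut-points for a minimum high biomarker value" and outer cuts give unbalanced groups. The evidence points the other way. In 100 simulated subjects with a true step at the median (13.2% vs 39.6%), scanning cuts from the 10th to the 90th percentile, the smallest p lands within 10 percentiles of the true cut in about 74% of trials. The largest difference does so in 46% and the largest odds ratio in 44%. At fixed N, penalising small, unstable groups is useful. SAP 11.1 also prefers at least 10 subjects per subgroup and calls for extra care when groups or events are few.

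**Conclusion.** The point holds for comparisons between analyses of different size: baseline against change, and objective response against duration of response. There, a p-value is a poor descriptive measure of relative strength. With the plan's own rates and sizes, an identical effect yields median p-values about ninefold apart. A truly stronger change marker is placed second in about 48% of trials by p, against 22% by observed difference. The second result rests on the assumed 8% vs 45%, and both rest on independent draws and on evaluable numbers near the planned 100 and 55.

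The point does not extend to choosing a cut-point within one analysis, and it does not show that effect estimates are missing from the plan. It concerns one sentence of interpretation. That sentence is worth correcting because, in a study with no formal test, it can decide which association is called strongest.

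**What to change.** Reword the sentence in SAP 11.1 along these lines: *Relative strength of association across biomarkers, time points and endpoints will be judged from effect estimates with 95% CIs, with the number of subjects (and events) shown. Estimates will be put on a common scale within each endpoint type: AUC or odds ratio per SD of log density for objective and durable response, hazard ratio per SD for duration of response, and correlation coefficient for tumor burden. Baseline density and change in density will be compared in subjects with both biopsies. Nominal p-values are secondary.*

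If log density is used, state how zero counts are handled; protocol 2.1 notes that about one-third of melanomas have few or no infiltrating T cells. Check the wording against the unredacted SAP 11.4 so that the two agree. No change to the cut-point analyses is proposed.

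The cost is SAP wording and a few extra output columns, with no new data. The price is precision: the comparison of baseline with change would rest on about 55 subjects instead of 100. The full-set baseline estimate can still be reported beside it.
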